3.4 RATIONALE FOR STUDY DESIGN

3.4.1 Rationale for Patient Population

Cohort 1 will enroll patients with resectable Stage III melanoma with measurable lymph node metastases (according to RECIST v1.1) that can be biopsied, and who have no history of in-transit metastases within the last 6 months. Enrolled patients must not have received prior immunotherapy for their disease.

This same patient population was enrolled in the OpACIN and OpACIN-neo studies, including the PRADO extension cohort. These studies evaluated the neoadjuvant (and adjuvant) combination of nivolumab and ipilimumab in patients with resectable melanoma. Neoadjuvant therapy was found to have a statistically significant and

clinically meaningful benefit as compared with adjuvant therapy (Rozeman et al. 2019; Blank et al. 2020; Rozeman et al. 2021). In addition, the safety profile of the treatment was found to be tolerable in an optimized treatment schedule.

Despite the recently demonstrated benefit of checkpoint inhibition therapy, there is a continuing need for treatment regimens that are more efficacious (i.e., broader and deeper pathologic response in the surgical specimen) and better tolerated for patients with resectable melanoma. The multiple treatment options in this study are expected to stimulate the immune system through a variety of mechanisms (see [Appendix 11](#) through [Appendix 16](#) for more details). The aim is to extend the benefit of CIT beyond that of current checkpoint inhibition to a larger population with resectable melanoma.

Cohort 2 will enroll patients with Stage IV melanoma who experienced disease progression during or after at least one but not more than two lines of treatment for metastatic disease. Up to two lines of checkpoint inhibition therapy (monotherapy or combination therapy) are allowed. Patients with BRAF-mutant disease may have received an additional line of targeted therapy (either before, intermittent with, or after the checkpoint inhibition therapy) or may have received targeted therapy and checkpoint inhibition therapy concurrently as one combination treatment. Patients with BRAF-mutant melanoma with rapidly progressive disease who have not been previously treated with approved targeted therapies are not eligible.

Novel combinations of compounds with a clinical and/or biological rationale for anti-melanoma activity that have not yet been tested clinically will be investigated in Cohort 2. Importantly, for individual compounds considered for novel combinations, safety and tolerability have been already established in other studies and a safe dose and schedule are available. The Cohort 2 safety run-in phase will assess the safety of the novel combination with regards to potential overlapping toxicities (see Section 3.1.4 for details).

3.4.2 [Rationale for Immunotherapy-Based Treatment beyond Initial Radiographic Progression](#)

In studies of immunotherapeutic agents, complete response (CR), partial response (PR), and stable disease (SD) have each been shown to occur after radiographic evidence of an apparent increase in tumor burden. This initial increase in tumor burden caused by immune-cell infiltration in the setting of a T-cell response has been termed pseudoprogression (Hales et al. 2010). In Study PCD4989g, evidence of tumor growth followed by a response was observed in several tumor types. In addition, in some responding patients with radiographic evidence of progression, biopsies of new lesions or areas of new growth in existing lesions revealed immune cells and no viable cancer cells.

In Cohort 1, because of the possibility of an initial increase in the size of metastatic lymph nodes caused by immune-cell infiltration in the context of a treatment elicited

T-cell response in the absence of unacceptable toxicity, patients who meet the criteria for disease progression in the target lymph node metastases per RECIST v1.1 while receiving treatment with a CIT drug will be permitted to continue study treatment until surgery. However, the appearance of novel, previously undetected non-lymph node lesions may indicate that the patient has in fact been understaged and rather presents with more advanced or Stage IV disease. Because of the potential for a response after pseudoprogression, this study will allow patients randomly allocated to immunotherapy-based treatment arms to continue combination treatment after apparent radiographic progression per RECIST v1.1, provided the benefit–risk ratio is judged to be favorable by the investigator (see criteria in Section 3.1.2). Patients should be discontinued for unacceptable toxicity or loss of clinical benefit as determined by the investigator after an integrated assessment of radiographic and biochemical data, local biopsy results (if available), and clinical status (see Section 3.1.2 for details).

3.4.3 Rationale for the Use of Modified RECIST for Immune-Based Therapeutics

Increasing clinical experience indicates that traditional response criteria (e.g., RECIST v1.1 and World Health Organization criteria) may not adequately assess the activity of immunotherapeutic agents because initial radiographic evidence of disease progression does not necessarily reflect therapeutic failure. Patients can experience a response in the presence of new lesions or after an increase in tumor burden. Thus, this study will employ iRECIST (Seymour et al. 2017; see [Appendix 2](#)), tumor response criteria that have been modified for unconventional tumor change patterns associated with CIT.

iRECIST was developed by the RECIST working group in an effort to create a common set of criteria that the CIT field could apply to clinical trials (Seymour et al. 2017). iRECIST accounts for responses that may occur following transient radiographic progression caused by immune-cell infiltration in tumors (leading to a transient increase in the size of existing lesions, including those that were previously undetectable and consequently appear as new lesions). iRECIST relies on collection of tumor assessment data after initial disease progression per RECIST v1.1.

Given the proposed immunomodulatory mechanism-of-action of atezolizumab and other CPIs and the possibility of observing delayed responses, exploratory efficacy endpoints will include analyses based on iRECIST. These analyses will allow for evaluation of iRECIST as an improved measure of the efficacy of immunotherapies relative to standard RECIST v1.1.

3.4.4 Rationale for Neoadjuvant Treatment in Melanoma in Cohort 1

Neoadjuvant therapy has several potential advantages over adjuvant therapy, and could even be superior to adjuvant therapy in this patient population. In particular, using neoadjuvant therapy could allow investigators to determine therapy efficacy in individual patients, which could guide the use of additional adjuvant therapy, if needed.

Neoadjuvant therapy could also reduce tumor burden before surgery, and the pathologic response data could be used as surrogate outcome markers for RFS and OS. In the case of T-cell checkpoint blockade, neoadjuvant therapies could have a potentially significant advantage. T-cell checkpoint-blocking antibodies enhance T-cell activation when an antigen is encountered. Drug exposure during the time the major tumor mass is still present may therefore potentially induce a stronger and broader tumor-specific T-cell response (Blank et al. 2018). Indeed, preclinical data provided support for the superior activity of T-cell checkpoint blockade when given before surgery (Liu et al. 2016).

Data from the recent OpACIN and OpACIN-neo studies show that two cycles of neoadjuvant ipilimumab plus nivolumab without additional adjuvant therapy induces durable RFS in more than 80% of patients, and further endorse pathologic response as a strong surrogate outcome marker for RFS (Rozeman et al. 2021).

3.4.5 Rationale for Pathologic Response Rate as Primary Endpoint in Cohort 1

The pathologic response to neoadjuvant therapy is a surrogate endpoint of improved patient outcomes in the treatment of several cancer types. The majority of neoadjuvant studies that are ongoing in melanoma are testing immunotherapy and use pathologic response as an endpoint (Mueller et al. 2021).

Several studies, including OpACIN and OpACIN-neo, have shown that pathologic response appears to be a strong surrogate marker for long-term benefit. A pooled analysis of the INMC confirmed that pathologic response strongly correlates with RFS and OS with neoadjuvant therapy in Stage III melanoma. It is further reported that particularly with combination immunotherapy, any degree of pathologic response with immunotherapy is sufficient to confer excellent survival.

Six neoadjuvant melanoma studies were conducted recently with BRAF/MEK-targeted therapy or PD-1-based immunotherapy, and demonstrated that neoadjuvant therapies achieve high pCR rates and RFS in Stage III melanoma. In the pooled analysis, pCR occurred in 40% of patients: 47% with targeted therapy and 33% with immunotherapy (43% combination and 20% monotherapy). pCR correlated with improved RFS (pCR 2-year 89% vs. no pCR 50%, $p < 0.001$) and OS (pCR 2-year OS 95% vs. no pCR 83%, $p=0.027$). In patients achieving a pathologic response with immunotherapy, very few relapses were seen (2-year RFS 96%), and no patient had died from melanoma at time of the report. With pCR from targeted therapy, the 2-year RFS was only 79%, and OS was only 91% (Menzies et al. 2021).

3.4.6 Rationale for Using Nivo+Ipi as Comparator in Cohort 1

No standard of care exists for neoadjuvant treatment of resectable melanoma. The highest pathologic response rates have been observed in Stage IV disease and in Stage III disease in the neoadjuvant setting with the combination of nivolumab and

ipilimumab (Menzies et al. 2021). As pathologic response (especially pCR, but also *near* pCR) emerges as a potential surrogate endpoint for RFS benefit, the combination of nivolumab and ipilimumab was chosen as the active comparator for this study. In addition, given the positive data in several studies and the approval of the combination of nivolumab and ipilimumab for patients with advanced melanoma, this combination was considered to be the best comparator for the anticipated patient population in this study (Wolchok et al. 2013; Sznol et al. 2014). Furthermore, a Phase III study with the objective of establishing nivolumab combined with ipilimumab as a standard of care option for neoadjuvant therapy is planned (NADINA Trial).

The recommended dose for advanced melanoma is 1 mg/kg nivolumab and 3 mg/kg ipilimumab. This study will use alternative dosing of 3 mg/kg nivolumab and 1 mg/kg ipilimumab because this dosing schedule induced a lower rate of immune-mediated toxicity in the OpACIN-neo study, and thus was identified as the optimal dosing regimen in the neoadjuvant setting (Rozeman et al. 2019).

Randomized studies evaluating immunotherapy combinations will allow us to identify safe and effective neoadjuvant treatments for patients with resectable melanoma while also significantly increasing our understanding of cancer biology.

3.4.7 Rationale for Biomarker Assessments

Blood samples for biomarker assessments will be collected at baseline and during the study. Changes in biomarkers in blood may provide evidence of biologic activity of the specific treatments and treatment combinations. Correlations between surrogate biomarkers in blood (such as tumor burden markers, cytokines, chemokines, immune cell subpopulations, gene expression, and ctDNA) and drug dose and efficacy and safety endpoints may allow for the development of a blood-based biomarker to help define future treatments and predict which patients are more likely to benefit from specific treatment combinations.

Baseline tumor tissue samples will be collected from all patients (except patients in the Cohort 2 safety run-in phase) by biopsy at screening. In addition, on-treatment tissue samples will be collected up to 72 hours prior to drug administration. If available, archival primary tumor tissue will be submitted from all patients.

Tumor samples will be evaluated for biomarkers such as tumor-infiltrating immune cells, PD-L1, CD8, and expression of targets specific to each drug combination. Evaluation of the tumor microenvironment in response to treatment within each arm, including changes in the number, locations, densities and functional status of tumor-infiltrating immune cells, could provide validation of the postulated mechanism-of-action, confirmation that an appropriate dose and exposure for the specific treatment combination have been achieved, *and/or response prediction capacity*. Differences in biomarkers and lymphocyte infiltration in baseline primary tumor compared to metastasis may be assessed.

Tumor tissue and blood samples may be analyzed through use of NGS methods such as whole exome sequencing (WES) to identify somatic mutations that are predictive of response to study drug, are associated with progression to a more severe disease state, are associated with acquired resistance to study drug, are associated with susceptibility to developing adverse events, or can increase the knowledge and understanding of disease biology.

4. MATERIALS AND METHODS

4.1 PATIENTS

4.1.1 Inclusion Criteria

Patients must meet all of the criteria outlined in Section [4.1.1.1](#) and Section [4.1.1.2](#) to qualify for Cohort 1. Patients must meet all of the criteria outlined in Section [4.1.1.1](#) and Section [4.1.1.3](#) to qualify for Cohort 2.

4.1.1.1 Shared Inclusion Criteria for Cohort 1 and Cohort 2

Patients must meet all of the following criteria to qualify for Cohort 1 and Cohort 2:

- Signed Informed Consent Form
- Age \geq 18 years at the time of signing Informed Consent Form
- ECOG performance status (PS) of 0 or 1
- Ability to comply with the protocol, in the investigator's judgment
- Availability of a representative tumor specimen that is suitable for biomarker testing via central laboratory

Baseline tumor tissue samples will be collected from all patients (except patients in the Cohort 2 safety run-in phase) by biopsy of a metastatic lymph node (Cohort 1) or other metastatic lesion (Cohort 2) at screening.

In addition, archival primary tumor tissue will be submitted from all patients. In exceptional cases where no archival primary tissue is available (e.g., for patients with unknown primary tumor), enrollment is permitted. For archival tissue, a formalin-fixed, paraffin-embedded (FFPE) tumor specimen in a paraffin block (preferred) with sufficient size and tumor content representation, preferably including the invasive margin, or, if available, at least 16 slides containing unstained, freshly cut, serial sections must be submitted along with an associated pathology report.

Refer to Section [4.5.9](#) and to the laboratory manual for additional information on tumor specimens collected at screening.

- Adequate hematologic and end-organ function, defined by the following laboratory test results, obtained within 14 days prior to initiation of study treatment:
 - ANC $\geq 1.5 \times 10^9/\text{L}$ (1500/ μL)
 - Lymphocyte count $\geq 0.5 \times 10^9 \text{ cells/L}$ (500/ μL)
Borderline machine lymphocyte counts may be confirmed by a manual count.
 - Platelet count $\geq 100 \times 10^9/\text{L}$ (100,000/ μL)
 - Hemoglobin $\geq 90 \text{ g/L}$ (9 g/dL)
 - AST, ALT, and ALP $\leq 2.5 \times \text{ULN}$ with the following exceptions:
 - For Cohort 2, patients with documented liver metastases: AST and ALT $\leq 5 \times \text{ULN}$.
 - For Cohort 2, patients with documented liver or bone metastasis: ALP $\leq 5 \times \text{ULN}$.
 - Total bilirubin $\leq 1.5 \times \text{ULN}$, with the following exception:
 - Patients with known Gilbert disease: bilirubin level $\leq 3 \times \text{ULN}$
 - Creatinine $\leq 1.5 \times \text{ULN}$ or creatinine clearance $\geq 30 \text{ mL/min}$ (calculated using the Cockcroft-Gault formula)
 - Serum albumin $\geq 25 \text{ g/L}$ (2.5 g/dL)
 - For patients not receiving therapeutic anticoagulation: INR and aPTT $\leq 1.5 \times \text{ULN}$
- For patients receiving therapeutic anticoagulation: stable anticoagulant regimen (i.e., no new thrombosis, thromboembolic event, or bleeding episode within 3 months prior to study treatment start)
- **Negative HIV test at screening, with the following exception: Patients with a positive HIV test at screening are eligible provided they are stable on anti-retroviral therapy, have a CD4 count $\geq 200/\mu\text{L}$, and have an undetectable viral load.**
 - Patients without a prior positive HIV test result will undergo an HIV test at screening, unless not permitted per local regulations.
 - Negative hepatitis B surface antibody (HBsAb), and negative total hepatitis B core antibody (HBcAb) test at screening. If a patient has a negative hepatitis B surface antigen (HBsAg) test and a positive total HBcAb test at screening, an hepatitis B virus (HBV) DNA test must also be performed to rule out active HBV.
 - Negative hepatitis C virus (HCV) antibody test at screening, or positive HCV antibody test followed by a negative HCV RNA test at screening
 - The HCV RNA test will be performed only for patients who have a positive HCV antibody test.
 - For women of childbearing potential: agreement to remain abstinent (refrain from heterosexual intercourse) or use contraceptive measures, as outlined for each specific treatment arm in [Appendix 11](#) through [Appendix 16](#).

- For men: agreement to remain abstinent (refrain from heterosexual intercourse) or use contraceptive measures, and agreement to refrain from donating sperm, as outlined for each specific treatment arm in [Appendix 11](#) through [Appendix 16](#).

4.1.1.2 Inclusion Criteria for Cohort 1

Patients must meet all of the following criteria to qualify for Cohort 1:

- Histologically confirmed resectable Stage III melanoma (T: T0, Tx or T1–4; N: cN1–3, pN1b/2b/3b; M: M0 according to AJCC-8 [Gershenwald et al. 2017]) and no history of in-transit metastases within the last 6 months

Patients may present with primary melanoma with concurrent regional nodal metastasis, or a history of primary melanoma or unknown primary melanoma with clinically detected regional nodal recurrence, and may belong to any of the following groups:

- Primary cutaneous melanoma with concurrent clinically/radiologically apparent regional lymph node metastases
- Clinically/radiologically detected recurrent melanoma at the proximal regional lymph node(s) basin
- Clinically/radiologically detected nodal melanoma (if single site) arising from an unknown primary
- Fit and planned for CLND (as assessed by surgeon prior to randomization according to local guidelines)
- Measurable disease (at least one target lesion) according to RECIST v1.1

At least one macroscopic lymph node metastasis (measurable according to RECIST v1.1) to be biopsied.

4.1.1.3 Inclusion Criteria for Cohort 2

Patients must meet all of the following criteria to qualify for Cohort 2:

- Life expectancy \geq 3 months, as determined by the investigator
- Histologically confirmed Stage IV (metastatic) cutaneous melanoma according to AJCC-8 (Gershenwald et al. 2017)
- Disease progression during or following at least one but no more than two lines of treatment for metastatic disease

Up to two lines of CPI therapy (monotherapy or combination therapy) are allowed. Patients with BRAF-mutant disease may have received an additional line of targeted therapy (either before, intermittent with, or after the CPI therapy), or may have received targeted therapy and CPI therapy concurrently as one combination treatment. Patients with BRAF-mutant melanoma with rapidly progressive disease who have not been previously treated with approved targeted therapies are not eligible. Patients who received adjuvant treatment with CPI therapy for localized melanoma require an additional line of CPI therapy in the metastatic setting. Patients who relapse or systemically progress

during or within 6 months of completion of adjuvant therapy are eligible and do not require an additional line of CPI therapy.

- Measurable disease (at least one target lesion) according to RECIST v1.1

At least one metastasis (measurable according to RECIST v1.1).

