4.5.9 Laboratory, Biomarker, and Other Biological Samples

4.5.9.1 Local Laboratory Assessments

For information about the timing of local laboratory assessments, please refer to the schedule of activities for screening ([Appendix 10](#)) or the appropriate treatment arm (Sections [A11–6](#) [Nivo + Ipi], [A12–6](#) [RO7247669 2100 mg], [A13–6](#) [Atezo + Tira], [A14–6](#) [RO7247669 2100 mg + Tira Cohort 1], [A14–8](#) [RO7247669 2100 mg + Tira Cohort 2], [A15–6](#) [RO7247669 600 mg], and [A16–6](#) [RO7247669 600 mg + Tira]).

Samples for the following laboratory tests will be sent to the study site's local laboratory for analysis:

- Hematology: WBC count, RBC count, hemoglobin, hematocrit, platelet count, and differential count (neutrophils, eosinophils, basophils, monocytes, lymphocytes, and other cells)

- Chemistry panel (serum or plasma): includes sodium, potassium, magnesium, chloride, bicarbonate or total carbon dioxide (if considered standard of care in the region), glucose, BUN or urea, creatinine, total protein, ferritin, albumin, phosphate, calcium, total bilirubin, ALP, ALT, AST, amylase, lipase, and LDH. In addition, adrenocorticotrophic hormone (ACTH), cortisol, S100, and erythrocyte sedimentation rate (ESR) will be assessed at screening and pre-surgery visits for patients enrolled in Cohort 1.
- Lipid panel: includes triglycerides, HDL, and LDL
- Coagulation: INR and aPTT
- Thyroid function testing: TSH, free T3 (or total T3 for sites where free T3 is not performed), and free T4
- Cardiac enzymes: troponin I or T
- C-reactive protein
- HIV serology, unless not permitted per local regulations
- HBV serology: hepatitis B surface antigen (HBsAg), hepatitis B surface antibody (HBsAb), total hepatitis B core antibody (HBcAb), and (if HBsAg test is negative and total HBcAb test is positive) HBV DNA

If a patient has a negative HBsAg test and a positive total HBcAb test at screening, an HBV DNA test must also be performed to determine if the patient has an HBV infection.
- HCV serology: HCV antibody and (if HCV antibody test is positive) HCV RNA

If a patient has a positive HCV antibody test at screening, an HCV RNA test must also be performed to determine if the patient has an HCV infection.
- EBV serology:
 - EBV VCA IgM
 - EBV VCA IgG or Epstein-Barr nuclear antigen (EBNA) IgG
 - EBV PCR (only if clinically indicated)
- Cytomegalovirus (CMV) serology: CMV IgM and IgG

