9.2 PROTOCOL DEVIATIONS

The investigator should document and explain any protocol deviations. The investigator should promptly report any deviations that might have an impact on patient safety and data integrity to the Sponsor and to the IRB/EC in accordance with established IRB/EC policies and procedures. The Sponsor will review all protocol deviations and assess whether any represent a serious breach of Good Clinical Practice guidelines and require reporting to health authorities. As per the Sponsor's standard operating procedures, prospective requests to deviate from the protocol, including requests to waive protocol eligibility criteria, are not allowed.

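### The hepatitis B inclusion criterion is internally inconsistent: everyone sent for HBV DNA testing is already ineligible, and the surface antigen result sets no eligibility condition

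*Combined protocol and SAP*

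**What the plan says.** Section 4.1.1.1 (Shared Inclusion Criteria) opens with a conjunctive rule: "Patients must meet all of the following criteria to qualify for Cohort 1 and Cohort 2". The hepatitis B bullet in that list has two sentences.

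- Sentence 1 requires: "Negative hepatitis B surface antibody (HBsAb), and negative total hepatitis B core antibody (HBcAb) test at screening".
- Sentence 2 begins "If a patient has a negative hepatitis B surface antigen (HBsAg) test and a positive total HBcAb test at screening" and continues that "an hepatitis B virus (HBV) DNA test must also be performed to rule out active HBV".

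Section 4.5.9.1 (Local Laboratory Assessments) puts HBsAg, HBsAb and total HBcAb on the screening panel and repeats the DNA step: "If a patient has a negative HBsAg test and a positive total HBcAb test at screening, an HBV DNA test must also be performed". Neither section says which DNA result makes a patient eligible.

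The next bullet, on hepatitis C, is built differently: "Negative hepatitis C virus (HCV) antibody test at screening, or positive HCV antibody test followed by a negative HCV RNA test at screening". The HIV bullet likewise states its exception outright.

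Section 9.2 (Protocol Deviations) says that "prospective requests to deviate from the protocol, including requests to waive protocol eligibility criteria, are not allowed".

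**The concern.** An inclusion criterion should let two sites with the same laboratory results reach the same decision. Here sentence 1 disposes of core-antibody-positive patients, while sentence 2 and Section 4.5.9.1 treat them as undecided until the DNA result is back. The marker in the DNA trigger (HBsAg) also differs from the surface marker in the requirement (HBsAb).

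Three things are at stake.

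- **Consistency of screening.** A site applying sentence 1 screen-fails every HBsAb-positive and every HBcAb-positive patient. A site following the DNA pathway might enroll an HBcAb-positive, DNA-negative patient and so create an eligibility deviation, with no prospective waiver available.
- **Reporting.** Section 6.2 summarizes major deviations from the entry criteria by arm, so differing site readings could reach the study report.
- **Safety screening.** The bullet does not make the antigen result a condition of entry, although it is measured.

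The criterion is shared by both cohorts. Cohort 1 has two added arms, and the synopsis says no Cohort 2 arm is currently open.

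**Working it through.** The plan has no figure to reproduce, and no power or error rate is involved. The check is a truth table.

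**Inputs**

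- Sentence 1 (Section 4.1.1.1): met if HBsAb is negative and HBcAb is negative.
- DNA trigger (sentence 2 and Section 4.5.9.1): HBsAg negative and HBcAb positive.
- All shared criteria must be met (opening line of Section 4.1.1.1).

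**All 2 × 2 × 2 = 8 profiles**

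| HBsAg | HBsAb | HBcAb | Meets sentence 1 | DNA test triggered |
|---|---|---|---|---|
| - | - | - | yes | no |
| - | - | + | no | yes |
| - | + | - | no | no |
| - | + | + | no | yes |
| + | - | - | yes | no |
| + | - | + | no | no |
| + | + | - | no | no |
| + | + | + | no | no |

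**Results**

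1. Two profiles meet sentence 1 and two trigger the DNA test; the overlap is 0. The trigger needs HBcAb positive and sentence 1 needs HBcAb negative, so no DNA result can change an eligibility decision.
2. All four HBsAb-positive profiles fail. The one that is negative on both other markers (HBsAg-/HBsAb+/HBcAb-) triggers no DNA test either, so it has no route to eligibility.
3. Of the four antigen-positive profiles, three fail sentence 1 through an antibody result. One, HBsAg+/HBsAb-/HBcAb-, meets the bullet.

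**Would one wrong word explain it?** Suppose HBsAb in sentence 1 were a slip for HBsAg. Sentence 1 would then need HBsAg negative and HBcAb negative. Both DNA-triggered profiles are still HBcAb-positive, so both still fail, and result 1 is unchanged. Swapping the marker alone does not repair the bullet.

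**Does other text resolve it?** The exclusion criteria in Sections 4.1.2.1 to 4.1.2.5 do not name hepatitis B or HBsAg. Section 4.1.2.1 excludes active infection that the investigator judges could affect patient safety, and laboratory findings that contraindicate an investigational drug. Section 5.1 says in general terms that actively infected patients are excluded. These may catch an antigen-positive patient. They do not admit an HBsAb-positive patient, and they do not settle the status of an HBcAb-positive, DNA-negative one.

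**The case against.** The strongest reply is that the two sentences can both be obeyed: exclude the core-antibody-positive patient and run the DNA test anyway. Sentence 2 orders a test and never says that a DNA-negative patient qualifies. That is right, so this is not a strict logical contradiction. But a test meant to rule out active infection at screening has no role in eligibility if its result cannot matter, and the inconsistency in function stands.

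A reader might draw four stronger conclusions, which the documents do not support.

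- **That the protocol admits patients with active hepatitis B.** Only one of four antigen-positive profiles meets the bullet. Section 4.5.1 requires all screening evaluations to be reviewed before enrollment, and the general exclusions in Sections 4.1.2.1 and 5.1 still apply. They are general and partly a matter of judgment, so they narrow the gap without closing it.
- **That vaccinated patients are barred.** The documents do not link hepatitis B vaccination to HBsAb. What the text supports is that patients HBsAb-positive at screening are excluded.
- **That screening is inflated by a calculable factor, or that deviations have occurred.** There is no antibody prevalence, no screen-failure count and no account of how sites read the bullet. Recruitment has proceeded, so the site consequences are possible, not shown.
- **That the treatment comparison is biased.** Under Section 4.2, eligibility is established before assignment, and the criterion is common to all arms. Nothing here points to bias in the pRR difference of Section 6.4.1.

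The wording is not a text-extraction fault: surface antibody is spelled out in the bullet, and the abbreviation list defines HBsAb and HBsAg separately.

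**Conclusion.** The point holds as an internal inconsistency in an operative eligibility rule. As written, the DNA result affects eligibility in none of the eight profiles, HBsAb-positive patients are excluded with no exception, and one antigen-positive profile is left to general exclusions. These are counts of logical profiles, not of patients, and say nothing about how common each profile is.

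The conclusion rests only on reading the bullet literally within a list whose items must all be met. Whether HBsAb was intended is unknown, and the point does not depend on it. The consequences are limited to consistency of screening across sites, who can enter the study, and a narrow gap in safety screening. Because waivers are barred and correction is cheap, the sponsor should correct it.

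**What to change.** Reconcile the hepatitis B bullet in Section 4.1.1.1 with Section 4.5.9.1 so that both use the same markers. State the eligibility consequence of each HBsAg, HBsAb, HBcAb and HBV DNA result, including the combination of positive HBcAb and negative DNA. The hepatitis C bullet already supplies a workable form: a primary result, or an alternative result followed by a named confirmatory one. Which results qualify is for the sponsor's medical team to decide; this review proposes no rule.

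The cost is one bullet in the next amendment and a clarification to sites. No new tests are needed, because Section 4.5.9.1 already provides for all three serology markers and the triggered DNA test.
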